9.5.4.3 Reporting of Events Associated with Special Situations

9.5.4.3.1 REPORTING OF ADVERSE EVENTS ASSOCIATED WITH STUDY DRUG OVERDOSE, MISUSE, ABUSE, OR MEDICATION ERROR

Adverse events associated with study drug overdose, misuse, abuse, and medication error refer to AEs associated with uses of the study drug outside of that specified by the protocol. Overdose, misuse, abuse, and medication error are defined as follows:

| | |
|------------------|--|
| Overdose | Accidental or intentional use of the study drug in an amount higher than the protocol-defined dose |
| Misuse | Intentional and inappropriate use of study drug not in accordance with the protocol |
| Abuse | Sporadic or persistent intentional excessive use of study drug accompanied by harmful physical or psychological effects |
| Medication error | Any unintentional event that causes or leads to inappropriate study drug use or subject harm while the study drug is in the control of site personnel or the subject |

All AEs associated with overdose, misuse, abuse, or medication error should be captured on the Adverse Event eCRF and also reported using the procedures detailed in Reporting of Serious Adverse Events ([Section 9.5.4.1](#)) even if the AEs do not meet serious criteria. Abuse is always to be captured as an AE. If the AE associated with an overdose, misuse, abuse, or medication error does not meet serious criteria, it must still be reported using the SAE form and in an expedited manner but should be noted as nonserious on the SAE form and the Adverse Event eCRF.

9.5.4.3.2 REPORTING OF STUDY-SPECIFIC EVENTS

Study-specific events (as detailed in [Section 9.5.1.5.2](#)) should always be considered serious important medical events and be entered on the Adverse Event eCRF and reported using the procedures detailed in Reporting of Serious Adverse Events ([Section 9.5.4.1](#)), even if the study-specific event does not meet other serious criteria.

9.5.4.4 Expedited Reporting

The sponsor must inform investigators (or as regionally required, the head of the medical institution) and regulatory authorities of reportable events, in compliance with applicable regulatory requirements, on an expedited basis (ie, within specific time frames). For this reason, it is imperative that sites provide complete SAE information in the manner described above.

9.5.4.5 Breaking the Blind

In the case of a medical emergency where the appropriate treatment of the subject requires knowledge of the study treatment given, the investigator may break the randomization code for an individual subject. In all such cases, the AE necessitating the emergency blind break will be handled as an SAE in accordance with the procedures indicated above. Any broken code will be clearly justified and documented. The medical monitor must be notified immediately of the blind break.

9.5.4.6 Regulatory Reporting of Adverse Events

Adverse events will be reported by the sponsor or a third party acting on behalf of the sponsor to regulatory authorities in compliance with local and regional law and established guidance. The format of these reports will be dictated by the local and regional requirements.

All studies that are conducted within any European country will comply with European GCP Directive 2005/28/EC and Clinical Trial Directive 2001/20/EC. All SUSARs will be reported, as required, to the competent authorities of all involved European member states.

9.5.5 Completion/Discontinuation of Subjects

A subject may elect to discontinue study drug or withdraw from the study at any time for any reason. All subjects who discontinue taking study drug prematurely for any reason will undergo an ED Visit within 7 days of their last dose of study drug (see [Section 9.1.2.2](#)). In addition, Follow-Up Visits will be scheduled 4 and 12 weeks after the last dose of study drug (Visit 19 and Visit 20, respectively) (see [Section 9.1.2.3](#)). See [Table 7](#) for full details of the assessments to be performed at these visits. Subjects who discontinue study drug prematurely will also be scheduled to return to the study site for each scheduled visit when clinical efficacy assessments are to be conducted (ie, at Visits 11, 14, 15, 16, 17, and 18, if these visits have not already been performed). At these visits, only clinical efficacy assessments (MMSE, CDR, ADAS-cog14, FAQ, CBB and ISLT) will be conducted. Subjects who discontinue early from study drug are considered on study as long as they return for their regularly scheduled clinical efficacy visits as outlined above. Subjects who discontinue study drug early (as opposed to subjects whose dosing with study drug is temporarily suspended under Medical Monitor guidance) will not be permitted to restart study drug.

The investigator will promptly explain to the subject involved that the study will be discontinued for that subject and will provide appropriate medical treatment and other necessary measures for the subject. A subject who has ceased to return for visits will be followed up by mail, phone, or other means to gather information such as the reason for failure to return, the status of treatment compliance, the presence or absence of AEs, and clinical courses of signs and symptoms.

Subjects who withdraw prematurely from the study will be withdrawn for 1 of these primary reasons: AE(s), lost to follow-up, subject choice, inadequate therapeutic effect, withdrawal of consent, pregnancy, study terminated by sponsor, or other. In addition to the primary reason, the subject may indicate 1 or more secondary reason(s) for withdrawal from the study. Study disposition information will be collected on the Subject Disposition eCRF.

A subject removed from the study for any reason may not be replaced.

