9.4.7 Prior and Concomitant Therapy

Medication (including over-the-counter medications) or therapy administered to the subject before the study (within 6 months of randomization) and during the study (starting at the date of informed consent) will be recorded on the Prior & Concomitant Medication eCRF or Non-Pharmacological Procedures eCRF. The investigator will record on the Adverse Event eCRF any AE for which the concomitant medication/therapy was administered. If the concomitant medication/therapy is being administered for a medical condition present at the time of entry into the study, the investigator will record the medical condition on the Medical History and Current Medical Condition eCRF.

Listings of prohibited and permitted drugs are provided in [Appendix 2](#). Prohibited medications are presented in [Listing 1](#), [Listing 2](#), [Listing 3](#), [Listing 4](#), [Listing 5](#), and [Listing 6](#). Medications that are permitted with restrictions are listed in [Listing 7](#), [Listing 8](#), and [Listing 9](#).

The following agents are not permitted before randomization (specific timeframes are shown below) and throughout the study until after the last treatment visit:

- Anticoagulants (eg, warfarin, digabatin) are not permitted for a period of 5 half-lives or 7 days (whichever is longer) before randomization
- Drugs which may cause QTc prolongation are not permitted for a period of 5 half-lives or 14 days (whichever is longer) before randomization
- Strong CYP3A4 inhibitors are not permitted for a period of 5 half-lives or 14 days (whichever is longer) before randomization
- Live vaccines are not permitted within 3 months before randomization. This does not apply to non-live/inactivated vaccines
- Ig therapy and biologic drugs are not permitted within 6 months before randomization
- Systemic or ocular immunosuppressive or immunomodulatory drugs are not permitted for a period of 5 half-lives or 60 days (whichever is longer) before randomization

Subjects taking AChEIs or memantine must meet the following criteria in order to be included in the primary analyses:

- On a stable dose for 12 weeks before the Baseline cognitive assessments at Visit 2
- Remain on a stable dose while on study

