9.5.1.3 Efficacy Assessments

9.5.1.3.1 PSYCHOMETRIC ASSESSMENTS

The timing of psychometric assessments is shown in [Table 6](#) and [Table 7](#). These assessments should be administered in the morning (or, if not possible, consistently at the same time of day) and should be completed before more invasive assessments or procedures (eg, physical examination, ECG, blood draws). The order of assessments is: MMSE, CDR, FAQ, ISLT (immediate recall), CBB, and ISLT (delayed recall) at Screening; and MMSE, CDR, ADAS-cog₁₄, FAQ, ISLT (immediate recall), CBB, and ISLT (delayed recall) at the Baseline Visit.

At visits where the CDR or FAQ are conducted, the investigator will determine whether the caregiver or informant must attend in person or whether telephone contact will be suitable, and will base this determination upon the functional ability of the subject among other factors.

The Derived Alzheimer's Disease Composite Score: The primary efficacy endpoint is the change from baseline in the derived ADCOMS at 18 months of treatment in MCI/Prodromal subjects.

The ADCOMS is derived from the ADAS-cog (4 items), the MMSE (2 items), and the CDR (all 6 items), described below. The ADCOMS is more sensitive to clinical progression compared with currently existing clinical batteries and requires smaller sample sizes for clinical studies in MCI/Prodromal AD or mild AD. It also shows sensitivity to treatment effects with AChEIs. The ADCOMS assesses both cognitive and functional domains and can be offered as a single primary clinical endpoint. The ADCOMS has a range from 0 to 1.97.

CogState Brief Battery: The CBB is a computer-based battery comprising 4 cognitive tests:

1. Detection – a simple reaction time test where the subject presses a key when the card is turned face up from a pack of cards (“Has the card turned over”). Speed of response is the measure.
2. Identification – a simple choice reaction time test where the subject presses 1 of 2 keys when the card just turned face up is either a red card or a black card (“Is the card red”). Speed of response is the measure.
3. One Card Back – a simple working memory test where the subject presses 1 of 2 keys when the card turned face up is either the card seen in the immediately previous trial or not (“Is the previous card the same”). Accuracy of response is the measure.

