| Centralized dermatological assessment via photography ^g | | | | | | | | | X | | | X | X | X | X | X | X | X | | X | X |
| Neurological examination ^h | | | | | | | | | | | | X | | X | | X | X | X | X | X | X |
| Ophthalmic examination ⁱ | | | | | | | | | | | | | | | | | | | | | X |
| Concomitant medications ^j | | X | X | X | X | X | X | X | X | X | X | X | X | X | X | X | X | X | X | X | X |
| 12-lead ECG ^k | | | X | | X | | X | | X | | | X | | X | | X | X | X | X | X ^e | X |
| Clinical biochemistry and urinalysis | | | X | | X | | X | | X | | | X | X | X | X | X | X | X | X | X ^e | X |
| Complete blood count | | X | X | X | X | X | X | X | X | X | X | X | X | X | X | X | X | X | X | X ^e | X |
| Blood samples for lymphocyte subset analyses ^l | | X | X | X | X | X | X | X | X | X | X | X | X | X | X | X | X | X | X | X ^e | X |
| Blood samples for Igs ^m | | | | | X | | X | | X | | | X | | X | | X | X | X | X | X ^e | X |
| Blood samples for isolation of PBMCs | | | X | | | | | | X | | | | | | | | | | | | X |
| Urine pregnancy test (females of CBP only) | X ⁿ | | | | | | | | X | | | X | X | X | X | X | X | X | X | | X |
| Blood sample for storage for immune status ^o | | | | | X | | | | X | | | X | | X | | X | X | X | X | X | X |
| CBB and ISLT ^p | | | | | | | | | X | | | X | X | X | X | X | X | X | X | X | |
| MMSE ^p | | | | | | | | | X | | | X | X | X | X | X | X | X | X | X | |
| CDR ^p | | | | | | | | | X | | | X | X | X | X | X | X | X | X | X | |
| ADAS-cog ₁₄ ^p | | | | | | | | | X | | | X | X | X | X | X | X | X | X | X | |

| Table 7 Schedule of Procedures/Assessments in Study 202: Randomization Phase (Visit 3 through Visit 20) | | | | | | | | | | | | | | | | | | | | |
|---|---------------|---|----|----|----|----|----|----|----|-----|-----|-----|-----|-----|-----|-----|-----------------|-----------------|---------------------------|-----------------|
| Phase | Randomization | | | | | | | | | | | | | | | | | | UNS Visit ^d | |
| Period | Treatment | | | | | | | | | | | | | | | | Follow-Up | | | |
| Visit ^a | 3 | 4 | 5 | 6 | 7 | 8 | 9 | 10 | 11 | 12 | 13 | 14 | 15 | 16 | 17 | 18 | ED ^b | 19 ^c | | 20 ^c |
| Day | 1 | 8 | 15 | 22 | 29 | 43 | 57 | 71 | 85 | 113 | 141 | 183 | 274 | 365 | 456 | 547 | | 575 | | 631 |
| Week | 1 | 2 | 3 | 4 | 5 | 7 | 9 | 11 | 13 | 17 | 21 | 27 | 40 | 53 | 66 | 79 | | 83 | | 91 |
| Weeks elapsed since first dose | 0 | 1 | 2 | 3 | 4 | 6 | 8 | 10 | 12 | 16 | 20 | 26 | 39 | 52 | 65 | 78 | | 82 | | 90 |

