- a: Visit 3 should be conducted 7 to 10 days after completion of the Baseline visit (Visit 2) assessments and confirmation of eligibility to continue in the study, unless additional time is required to take Exclusion Criterion #19 into account. A window of ± 3 days will be permitted for Visit 4 to 14 inclusive. A window of ± 10 days will be permitted for Visit 15 to 18 inclusive. A window of ± 3 days will be permitted for the Follow-Up Visits. If use is made of the permitted visit windows, every effort should be made to bring the subject back in line with the "weeks elapsed since first dose" at subsequent visits.
- b: Subjects who discontinue taking study drug prematurely for any reason will undergo an ED Visit within 7 days of their last dose of study drug. In addition, Follow-Up Visits will be scheduled 4 and 12 weeks after the last dose of study drug (Visit 19 and Visit 20, respectively). Subjects who discontinue study drug prematurely will also be scheduled to return to the study site for each scheduled visit when clinical efficacy assessments are to be conducted (ie. at Visits 11, 14, 15, 16, 17, and 18, if these visits have not already been performed). At these visits, only clinical efficacy assessments (MMSE, CDR, ADAS-cog₁₄, FAQ, CBB, and ISLT) will be conducted. Regularly scheduled clinical efficacy visits do not need to be attended if they fall within 8 days (visit window) after the Early Discontinuation Visit or within ± 8 days of either of the Follow-Up Visits (Visit 19 and Visit 20). Subjects who discontinue early from study drug are considered on study as long as they return for their regularly scheduled clinical efficacy visits as outlined above.
- c: All subjects, regardless of whether they complete all 18 months of treatment or discontinue study drug prematurely, will complete 2 posttreatment Follow-Up visits; one 4 weeks after the last dose of study drug and a second 12 weeks after the last dose of study drug (Visit 19 and Visit 20 respectively). If clinically indicated, more frequent safety assessments can be made as UNS assessments or visits during the posttreatment Follow-Up period.

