9.7.1.5 Prior and Concomitant Therapy

All investigator terms for medications recorded in the eCRF will be coded to an 11-digit code using the World Health Organization Drug Dictionary (WHO DD) (Mar 2014). The number (percentage) of subjects who took prior and concomitant medications will be summarized on the Safety Analysis Set by treatment group, Anatomical Therapeutic Chemical class, and WHO DD preferred term. Prior medications will be defined as medications that stopped

before the first dose of study drug. Concomitant medications will be defined as medications that (1) started before the first dose of study drug and were continuing at the time of the first dose of study drug, or (2) started on or after the date of the first dose of study drug up to the date of the last dose. All medications will be presented in subject data listings.

Medications taken within the 12-week Follow-Up period will also be recorded.

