9.7.1.6.1 PRIMARY EFFICACY ANALYSIS

Primary analysis of primary endpoint

The primary analysis will be based on MCI/Prodromal subjects from the FAS with the prespecified censoring rule applied. The primary endpoint is the change from baseline to 18 months in the derived ADCOMS. The dose-response of the primary endpoint is modelled with a first-order normal dynamic linear model, where Normal and Inverse-Gamma priors are used. The primary efficacy analysis will calculate the Bayesian posterior probability that the dose identified is the most likely ED₉₀ dose that achieves 25% improvement over the placebo arm. At each interim analysis and the final analysis, 2 Bayesian probabilities will be summarized for each active dose: the probability it is the ED₉₀ dose and the probability of achieving 25% improvement over the placebo arm.

For the clinical efficacy data (ie, derived ADCOMS, MMSE, CDR, ADAS-cog, CBB, ISLT, and FAQ) subjects will be censored at the time of initiation of treatment with AChEIs or memantine, if they were not on these medications at the time of Baseline cognitive assessment (Visit 2), and will be censored at the time of dose adjustment of AChEIs or memantine if they were already on stable treatment with these medications at the time of Baseline cognitive assessment (Visit 2). The value of the primary endpoint for censored subjects will be imputed using data up to the censoring time and Bayesian longitudinal modeling.

Sensitivity analysis of primary endpoint

After unblinding, the primary endpoint will be analyzed using the Bayesian methods described above as well as conventional statistical methods. The following additional Bayesian analyses will be conducted as sensitivity analyses:

- The primary endpoint will be analyzed regardless of initiation of treatment, or dose adjustment, with AChEIs or memantine using the same Bayesian analysis method as primary analysis. This is an intent-to-treat analysis without any censoring.
- In case of early success, the primary analysis as well as the above sensitivity analyses will be repeated after all subjects have completed 18 months of treatment or have been lost to follow-up.

Statistical methods for the final conventional analyses will use a mixed-effects model with repeated measures (MMRM) on the change from baseline in the derived ADCOMS at

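### After Visit 20 the primary AChEI/memantine censoring rule has no assured data source for subjects who stop study drug before about Week 66, because their return visits are limited to efficacy scales while Section 9.4.7 calls for medication to be recorded throughout the study

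*Protocol*

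**What the plan says.** **Content of the return visits.** Section 9.5.5 brings early discontinuers back for each remaining efficacy visit among Visits 11, 14, 15, 16, 17 and 18, and states: "At these visits, only clinical efficacy assessments (MMSE, CDR, ADAS-cog14, FAQ, CBB and ISLT) will be conducted". Section 9.3.3 and Table 7 note b repeat the restriction ("At these visits, only clinical efficacy assessments"). Concomitant medication is not in the list. The file also holds protocol text that brings these subjects back at Weeks 53 and 79 only. It too limits the visits to efficacy scales, so the point does not turn on which schedule is read.

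**Status of these subjects.** They "are considered on study as long as they return for their regularly scheduled clinical efficacy visits" (Section 9.5.5).

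**Medication recording.** Section 9.4.7 says medication taken "during the study (starting at the date of informed consent) will be recorded on the Prior & Concomitant Medication eCRF". The Table 7 row "Concomitant medications ^j" is marked at Visits 4 to 18, the ED Visit, Visits 19 and 20, and unscheduled visits. Section 9.7.1.5 defines concomitant medication as running to the last dose and adds: "Medications taken within the 12-week Follow-Up period will also be recorded".

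**What the analysis needs.** Under Section 9.7.1.6.1, "subjects will be censored at the time of initiation of treatment with AChEIs or memantine" if they were not taking them at baseline, and at dose adjustment if they were. The month-18 value is then imputed from data before censoring. On the endpoint itself, Section 9.5.1.3.1 says of the ADCOMS: "It also shows sensitivity to treatment effects with AChEIs".

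**The concern.** The censoring rule is only as good as the dates that feed it. For a subject on study drug, those dates come from a medication review at every visit. For a subject who has stopped, the visit instructions, read literally, provide no such review once Visit 20 has passed, although ADCOMS is still being collected.

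Take a subject who stops at month 4 and starts donepezil at month 9. A site that follows Table 7 note b has no scheduled step at which to enter the start date. The later ADCOMS values could then go into the primary analysis uncensored. The same start in a subject still on study drug would be censored and imputed, so one event would be handled in two ways depending on treatment status.

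These ADCOMS data drive the 80% success criterion, the binding futility rule and the adaptive allocation. A date that was never collected cannot be recovered by a statistical analysis plan.

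**Working it through.** The plan states no figure on this point, so there is nothing to reproduce. The check sets the visit rules against each other and then works out by week arithmetic which follow-up time is uncovered.

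**Inputs**
- Efficacy visits at Weeks 12, 26, 39, 52, 65 and 78 after first dose (Table 7).
- Visit 20 at 12 weeks after the last dose (Section 9.5.5).
- Efficacy visits within ±8 days of Visit 19 or 20 may be skipped (Section 9.3.3, Table 7 note b).
- Maximum of 500 MCI/Prodromal subjects (Section 9.7.2.1).
- 20% attrition at 18 months. Section 9.7.2.1 gives this for the vMRI power only, so using it as a rate of stopping study drug is an assumption, shown with a range of 10% to 30%.

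**Step 1: who is fully covered.** Scheduled medication review reaches last dose + 12 weeks. It reaches Week 78 if the last dose is at or after 78 − 12 = Week 66.

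**Step 2: uncovered time.** Gap = 78 − (stop week + 12). Skippable visits are removed.

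| Stop (week) | Visit 20 (week) | Gap to Week 78 (weeks) | Efficacy visits after Visit 20 (weeks) |
|---|---|---|---|
| 12 | 24 | 54 | 26, 39, 52, 65, 78 |
| 26 | 38 | 40 | 52, 65, 78 |
| 39 | 51 | 27 | 65, 78 |
| 52 | 64 | 14 | 78 |
| 66 or later | 78 or later | 0 | none |

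**Step 3: how many are exposed.** If stops are spread uniformly over 78 weeks (assumption), 66/78 = 0.846, so 85% of discontinuers have month 18 after Visit 20. Allowing for the 8-day waiver, (66 − 8/7)/78 = 0.83. If all of them keep attending (the maximum case), the number exposed is 500 × stopping rate × 66/78:
- 10% stop: 42 subjects
- 20% stop: 85 subjects
- 30% stop: 127 subjects

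**Step 4: how many could escape the rule.** Only exposed subjects who start or change an AChEI or memantine matter. The protocol gives no rate. With an assumed 10% to 40% and 20% stopping, 0.20 × 0.846 × (0.10 to 0.40) = 1.7% to 6.8% of month-18 values. This is a ceiling: it supposes that every such event goes unrecorded.

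**The case against.** The strongest reply is that the protocol already requires the data. Section 9.4.7 sets no end to recording at last dose or Visit 20, and returning discontinuers count as on study. The list in Section 9.5.5 can be read as saying which tests are run, not as ending a standing eCRF duty. Where the protocol wants a cut-off for these subjects it writes one: AE collection and SAE solicitation stop 3 months after last dose (Section 9.5.1.5.1). No such stop is written for medication. Section 9.7.1.5 adds the 12-week period to a definition that otherwise ends at last dose, so it is not a stated limit. Section 9.5.7 has the investigator ask at each visit about care from another physician. CRF Completion Guidelines, which are not shown, may settle the matter.

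Much of this stands. A reader might infer that medication is not collected after discontinuation, or that the censoring rule cannot be applied to early discontinuers. The documents do not support either. Medication is reviewed at the ED Visit and Visits 19 and 20, the rule works in that window, and Section 9.4.7 points to recording beyond it.

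The reply does not remove the conflict. Three places tell the site to do only the efficacy scales. Section 9.5.7 serves to inform the other physician and asks for no drug name, start date or dose-change date. Appendix 2, Listing 7 asks for a stable dose of cognitive enhancers only up to the second Follow-Up Visit, which for a discontinuer is Visit 20.

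It is also fair to object that bias is unproven. Safety stopping rules on lymphocytes, infection, rash and QTcF make more stopping on active drug plausible, and a reader might infer that missed AChEI use would flatter the active arms. The protocol gives no rates by arm. Discontinuers on active arms are off drug, which may dilute an effect, and declining placebo subjects may start an AChEI more often. Even with assumed stopping of 30% on active and 15% on placebo, the arms differ by (0.30 − 0.15) × 0.846 × (0.10 to 0.40) = 1.3 to 5.1 percentage points of subjects. If an AChEI removed 25% of placebo decline (assumption), the distortion would be about 0.3 to 1.3 percentage points, well short of the 25% criterion.

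Finally, the analysis without censoring needs no medication dates. It is, however, a sensitivity analysis and does not drive success, futility or allocation.

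**Conclusion.** The point holds as an internal conflict that leaves the primary censoring rule without an assured data source in a defined period: after Visit 20, for subjects who stop study drug before about Week 66. The rule is covered by schedule up to Visit 20, and in full for later stops. The conflict itself rests on the text alone. The count of up to about 85 of 500 exposed subjects rests on 20% stopping, uniform stopping times and complete attendance. It counts subjects at risk of a missed date, not subjects misclassified.

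Neither the size nor the direction of any effect on the ADCOMS comparison can be established from the protocol, and no claim of bias toward a false success should be made. The matter is still worth correcting before data accrue, because the gap affects the primary analysis and the missing dates could not be supplied afterwards.

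**What to change.** In Sections 9.3.3 and 9.5.5 and in Table 7 note b, state that AChEI/memantine use (drug, start date, dose-change date) is asked about and entered on the Concomitant Medication eCRF at every post-discontinuation efficacy visit through month 18. Add to Section 9.7.1.5 that recording of these drugs continues through the last efficacy visit. This reconciles the visit instructions with Section 9.4.7 and changes no clinical rule.

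Cost: one question to the subject or informant at visits already scheduled, a minor protocol amendment and a small change to the eCRF visit matrix. No extra visits are needed.
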